**3. Abstract:**

Increasing numbers of veterans are experiencing executive dysfunction due to a mild traumatic brain injury (mTBI). Executive dysfunction interferes with participation in home and work activities. Therefore, an effective intervention is needed that will provide significant and long-lasting improvement in the everyday lives of our veterans. Goal Management Training (GMT), an intervention that teaches a five-step strategy to improve planning and organization, has demonstrated promising results (Levine et al., 2000; 2007). However, there are several weaknesses regarding validation of the GMT in individuals with TBI. Therefore, the proposed study is needed to determine the effect of the 10-session GMT on veterans with mTBI. This study will 1) administer the 10-session GMT to individuals that have an objective executive dysfunction; 2) due to mTBI; 3) use probes designed to measure the activities trained in GMT, along with a measure of generalization; and 4) determine the number of subjects needed to demonstrate a treatment effect in a future randomized clinical trial.

**4. Background:**

Brain Injury has become the signature wound of Operation Iraqi Freedom (OIF) and Operation Enduring Freedom (OEF). An estimated 20,000 military personnel have been wounded in action primarily due to blasts (US, 2006). However, an even larger number are thought to have suffered a mild traumatic brain injury (mTBI) that was left undetected (Lew, 2005). A mTBI is diagnosed if any of three following criteria are met: 1) loss of consciousness less than 30 minutes with a Glasgow Coma Scale of 13 or above; 2) any loss of memory for events immediately before and after the event (not longer than 24 hours); any alteration of mental state at the time of accident; 3) any focal neurological deficits that may, or may not, be transient (ACRM, 1993). Of an at risk group evaluated at Walter Reed during 2003-2004 an estimated 59% suffered at least a mild TBI while in combat (Warden, 2005). It is known that over 2 million civilians sustain a TBI each year, of which an estimated 85% are mild (Sherer and Novack, 2003). However, this figure may be an underestimation, since some individuals that sustain a mild TBI do not seek treatment.

The problems that result from mTBI are diverse. During the acute stage individuals may experience obvious problems with attention, verbal retrieval, forgetfulness, headache, dizziness, irritability, drowsiness, sleep disturbances and fatigue (Ponsford, 2000). In addition, military personnel also suffer emotional issues such as PTSD, depression and anxiety disorders (Lew, 2005). While the majority of individuals with

mTBI are thought to totally recover within the first three months, several studies have found up to 48% continue to experience one or more symptoms up to a year after the injury (Alves, 1993; Jacobson, 1995). For example, Drake et al. (2000) found in a military sample that 46% were not able to return to their previous duty after three to fifteen months; with memory and executive functions impairments as the greatest risk factor.

The chaos and trauma that occur when an explosive device is detonated make it difficult to follow the diagnostic criteria outlined above. Even so, military personnel exposed to a blast may suffer a mild TBI because the brain is especially susceptible to the “blast over pressurization” that affects fluid filled organs of the body (Mayorga, 1997). Exposure to a blast may cause diffuse axonal damage, as well as damage sustained from being thrown or having objects hit the head (Lew, 2005). The frontal lobes are most susceptible to injury due to the contact of the bony orbital surface to the frontal lobes and the frontal poles (Damasio & Anderson, 2003). Therefore, the diffuse axonal damage and contusions will occur prominently in the frontal lobes as well as other cortical and subcortical structures, which is evident in the cognitive deficits following a mTBI.

Executive functions are most commonly affected by damage to the frontal lobes. They can be disrupted by damage to the focal areas in the frontal lobes or to the frontal-subcortical circuits that integrate cognitive, self-regulatory, and emotional behavior (Stuss, 2007). In fact, disorganization as a result of executive dysfunction is the most common complaint about individuals with TBI (Mateer, 1987). The self-regulation of behavior is less necessary in well-learned activities that become automatic but is more necessary in new activities that require inhibition of an over-learned plan so that a new problem-solving strategy can be developed. A new plan requires the ability to maintain intentions as well as the execution of those intentions (Levine, 2000). After frontal injury, intention and action can become dissociated; individuals with frontal lobe damage may be able to tell you the appropriate action to take, but do not follow that action (Luria, 1966). Several steps need to be coordinated for an individual to achieve his/her intentions. First the difference between the current state and the desired state must be detected. Second, the steps needed to reach that desired state must be formulated. Third, the desired state must be kept in mind while resisting other distractions. Fourth, the barriers that occur along the way must be overcome until finally the goal is achieved. Once the goal is achieved, the result must be evaluated. Duncan (1986) refers to the inability to complete step 3 as “goal neglect”. In order to be able to live independently, we must be able to keep in mind what we are doing, avoid distractions, respond to novel problems in new ways while inhibiting the ineffective way we have responded in the past, and evaluate how well we did. Individuals with executive dysfunction will have difficulty performing the tasks necessary to deal with novel situations in an unstructured setting.

Given the numbers of military personnel who may be struggling with executive dysfunction, an effective intervention to improve executive functions is needed. However, there are no treatments for executive dysfunction in mTBI that have been rigorously investigated. Robertson (1996) developed a treatment package called goal management training (GMT) based on Duncan’s theory of “goal neglect”. GMT is a 7-session (2 hours/ session) interactive module that is presented in a group format. A 5-

stage strategy is taught to the participants and is then incorporated into tasks practiced in the group session as well as in tasks each participant is to practice at home. The 5-stage process consists of “stop-what am I doing”, “define the goal”, “list the steps”, “learn the steps”, then “check-am I doing what I planned”. Levine validated the GMT by randomly assigning 30 TBI patients to either a one-hour version of GMT or motor skills training (Levine et al. 2000). The one-hour GMT was associated with improvements (being more careful as demonstrated by taking longer to complete the task after training) in paper and pencil tasks (proof reading and grouping) that simulated tasks requiring cognitive control. Since then, Levine et al. have modified the GMT module and increased the length of training to seven, two-hour sessions (14 hours total) (Levine et al., 2007). To date the only published use of this expanded GMT has been with an elderly sample, embedded in a larger rehabilitation package. The expanded version (modified GMT) may offer promise to the mTBI population as well.

The proposed study is needed to determine the effect of the expanded GMT in veterans with mild TBI. 40-North Florida/South Georgia, Operation Enduring Freedom/Operation Iraqi Freedom/Operation New Dawn (OEF/OIF/OND) Veterans will be recruited who meet criteria for TBI (ARCM, 1993) and have current executive dysfunction.

Two screening measures, Delis-Kaplan Executive Function Test System (D-KEFS) color word interference test and the Stop Signal Task will be used to select individuals that demonstrate deficits in inhibition which is within the domain of executive function.

The Computerized Tower of London will be used to assess the improvement of inhibition as a result of the intervention. To measure the effect of the GMT on observations of executive functioning in the home environment (generalization) the Behavior Inventory of Executive Functioning in Adults (BRIEF-A) was selected. The BRIEF-A is a global measure of executive functioning and will demonstrate whether improvements in simulated tasks generalize to overall functioning as observed by a proxy in the home.

In addition to improved measures, the current 7-session/14-hour version of the GMT is the same as the one-hour version, however, the expanded version allows for additional practice of the learned strategies in both the group setting and in the home setting. The increased practice may decrease the effort needed to apply the strategies and increase the use of the strategies beyond the therapy sessions. In fact, Robey (1998) demonstrated that two or more hours of therapy a week produced a greater change than therapy delivered less than one and a half hours per week. Therefore, the expanded version is anticipated to show a stronger effect than the 1-hour GMT. Turner and Levine (2004) predicted that individuals with mild TBI would be able to apply the strategies learned in GMT easier than individuals with moderate or severe TBI. Therefore, it is expected that the proposed study will produce a magnified effect over the Levine et al. (2000) study by using improved measures, using a longer treatment of 20 hours instead of one hour, and applying the intervention to individuals with mild TBI versus moderate and severe TBI.

## **5. Specific Aims:**

Specific Aims: The purpose of this Phase I study is to test an innovative treatment for executive dysfunction in veterans with mTBI that utilizes formalized and manualized procedures that can be exported for use in a subsequent randomized clinical trial.

### **Aim 1.**

#### **Aim 1 is to test the benefits of GMT for improving executive function.**

Hypothesis 1a: GMT will significantly improve problem solving ability compared to the control group (primary measure: time to completion on the Tower of London (cTOL). Since PTSD is prevalent and a potentially influencing co-morbidity, we will investigate whether there is a significant interaction between treatment group and PTSD severity.

Secondary measures include number of optimal moves on the TOL; and measures derived from the Stop Signal Task (SST; a measure of inhibition control).

Exploratory Hypothesis 1.a. GMT will significantly improve everyday activities that require executive function skills (primary measure: Behavior Rating Inventory of Executive Function-Adult version, secondary measure: CRIS).

**Analysis Plan for Hypothesis 1. and Hypothesis 1.a.** To test the first specific aim (hypothesis 1), the primary analysis will use two sample t-test to compare group A (intervention) and group B (control) on improvements in time to completion on the TOL. In addition, as an exploratory analysis, we will perform a regression analysis that includes treatment group, PTSD severity and their interaction as independent variables, to adjust for PTSD severity and to investigate whether there is interaction between treatment group and PTSD severity. Similar analyses will be performed for hypothesis 1 for secondary outcome variables of change in index of optimal moves on the TOL and reaction time (RT) and accuracy on SST. To test hypothesis 1a, exploratory *tertiary analysis* using paired t-tests will determine whether treatment effect generalizes to executive function performance in everyday activities (BRIEF-A) or engagement in community participation (CRIS).

### **Aim 2**

Aim 2 is to investigate factors which affect response to treatment.

Hypothesis 2. Baseline cognitive ability, depression, sleep, and presence of PTSD will have a significant effect on response to treatment.

Analysis Plan for Hypotheses 2. To test the second specific aim, a general linear regression will be used to determine whether any of the four factors is associated with response to treatment. The analysis will be restricted to the participants assigned to the intervention group. The dependent variable for the regression model will be 'time to completion' on the TOL, and the independent variables will be CWI, BDI-II, PCL-M and PSQI scores.

## **6. Research Plan:**

To determine the effect of GMT on veterans with mTBI the following research will be conducted. Clinical staff from the NF/SG VHS will hand out recruitment flyers or refer OEF/OIF/ONF veterans diagnosed with mTBI to the Principal Investigator. Referred Veterans will be contacted by the PI or interested Veterans will contact the PI. Veterans that meet the inclusion/exclusion criteria will be scheduled to obtain consent. Once

consent has been obtained the veteran will be scheduled for the first screening visit. Veterans that meet inclusion criteria will be randomly assigned to either treatment or control groups, in a ratio of 38:16. In addition, the Pocock-Simon covariate adaptive randomization procedure will be used so that, for each PTSD severity category within each of the two sites, approximately 70% (38/54) of subjects are assigned to treatment group; consequently, there will be approximately equal proportion of PTSD subjects assigned to the treatment and control groups within each of the two study sites. Each veteran will complete testing prior to a 10-week intervention or control period; after intervention or control period; and at a one-month follow-up. Intervention will be offered to participants in the control group once testing is complete.

Participants will also be recruited and run in a parallel study in Durham under a Durham VA IRB approval. A total of 168 participants are anticipated to be enrolled in both Gainesville and Durham. Data from Durham will be entered in a VA share drive that both Gainesville and Durham staff can access. Data will not be transferred.

Table # 2 Study Design

	1 st Measure	GMT/Wait	2 nd Measure	3 rd Measure
Group A (n=38)	Pre-treatment testing	GMT/FP 10 wks	Post-treatment testing	Follow-up testing
Group B (n=16)	Pre-Control testing	Control (Brain Health Workshop) 10 wks	Post-control testing	Follow-up Control testing

Methods

Subjects

*Proxy/Informant: patient will select a person to answer a questionnaire on their executive function that observes the patient at least 2-3 times a week and is at least 18 years of age.*

Patient Inclusion Criteria:

- Diagnosis of Mild TBI or concussion by a physician or neuropsychologist in the medical record compliant with the American Congress of Rehabilitation Medicine; any of three following criteria are met: 1) loss of consciousness less than 30 minutes with a Glasgow Coma Scale of 13 or above; 2) any loss of memory for events immediately before and after the event (not longer than 24 hours); any alteration of mental state at the time of accident; 3) any focal neurological deficits that may, or may not, be transient (ACRM, 1993).
- Executive dysfunction determined by at least 1.5 standard deviation below the average scaled score (corrected for age) on either the Delis-Kaplan Executive function System (D-Kefs) Color Word Interference Test, or the EXAMINER flanker task.
- Age 18 to 55 years
- At least 4 months post injury
- Family member or friend that is willing to provide feedback

Exclusion Criteria:

- History of pre-morbid learning disability
- History of psychiatric diagnosis sufficiently severe to have resulted in inpatient hospitalization.
- Neurological disease unrelated to TBI (seizure disorder, stroke, ADHD)
- Score < 90 on National Adult Reading Test (NART)
- Failure of validity testing on either the Test of Memory Malinger (TOMM),. Score of 45 or less on TOMM Trial 2 or retention trial.
- Reported alcohol or substance abuse within the past year
- Reported involvement in current litigation
- Recent change of medications for seizures, depression or memory.
- Currently enrolled in other cognitive therapy that cannot be discontinued
- Does not speak English fluently
- Not competent to provide consent (also, not able to demonstrate understanding of expectations of study and potential risks of participation).

### *Procedures*

Intervention: The GMT is a 7-session intervention has been modified to a 10-session (2 hours/ session) interactive Power Point module that is presented in an individual or group format. Sessions 5, 6 and 7 have been split into two sessions each with time added to set-up and review functional practice. If a group format, the subject will be incorporated into a therapy session with 3-5 other participants (either other clinical patients or research participants diagnosed with TBI). During each session, a 5-stage strategy is taught to the participants. The 5-stage process consists of “stop-what am I doing?”, “define the goal”, “list the steps”, “learn the steps” then “check-am I doing what I planned”. The strategy is then incorporated into tasks practiced in the group session as well as in tasks each participant is to practice at home. The participants discuss utilization of the strategies and support the other members in the group. Friends or family members will participate in a training session prior to beginning GMT with the subject. The family member will be called each week during the GMT and asked to report whether the subject had an easy or difficulty time completing the homework assignments each week.

*Simulated Practice In The Laboratory:* Tasks during GMT training include exercises such as: 1) clapping to words while inhibiting clapping to a targeted word; 2) card sorting; 3) decision making and planning in order to complete five activities within a four minute time span; 4) Catalog Task; and 5) Book keeping task. The exercises start with relatively easy tasks and progress to more complex tasks. Participant’s strengths and weaknesses are discussed. Improvements are identified and reinforced as they learn more efficient planning and problem solving. The following steps are taught during simulated tasks: 1) Identify Main Goal; 2) Break down task into sub-goals and steps for each goal; 3) List supplies needed; 4) Recognize potential barriers to completing goal; 5) Determine strategy to accomplish task; 6) Prepare to begin task with “presence of mindedness” exercise; 7) State goal out loud; 8) Begin task and stop self frequently to state main goal out loud and check to be sure one is working toward the goal (on target).

*Functional Practice with Smartphone Technology:* In addition to GMT in the lab, three tasks will be first practice in the lab, than practiced at home. Participants will

select from the following: meal planning and shopping; planning a party; building a birdhouse; or paying monthly bills. A Smartphone application (AP) specifically developed to utilize the strategies taught in GMT will be loaded onto the participant's Smartphone (iPhone, iTouch, or Droid). Veterans that do not already possess one of the devices will receive one as part of their clinical service through prosthetics. Training will begin during the first session to learn the features of the technology they will need (calendar, list, alarms) using Michelle Wild's standardized learning procedure outlined in her guide books (<http://pda4memory.com>) that have been designed to train individuals with TBI how to use Smartphones. Participants will use the application features to break down tasks, estimate time to complete, check off each step as completed, respond to visual/vibrating alert of "Goal" and respond to alert if "On Target". Information, such as accuracy of planned steps, time to complete task, and number of distractions from goal will be collected by the AP. Data will not be electronically transferred; the participant's performance in functional practice at home will be reviewed and documented at the next lab session.

*Control Group Intervention.* The Brain Health Workshop (BHW; Levine 2011) was developed specifically for consistency with GMT session length and contact with the facilitator (Levine, 2011). BHW is an education presentation on brain function and cognitive principles of learning. Information about stress reduction, sleep hygiene, energy management, exercise and communication are covered, with homework and quizzes on information covered.

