**Table 1: Testing Schedule**

Screening	Pre-Treatment	Post Treatment #	One-Month f/u#
D-KEFs Color-Word Interference Test		D-KEFs Color-Word Interference Test	D-KEFs Color-Word Interference Test
NART	*BRIEF-A	*BRIEF-A	*BRIEF-A
TOMM	PSQI	PSQI	PSQI
	Tower of London	Tower of London	Tower of London
EXAMINER	EXAMINER	EXAMINER	EXAMINER
PCL-M	RBANS	RBANS	RBANS
	Stop-Signal Task	Stop-Signal Task	Stop-Signal Task
	Beck Depression Inventory-II	Beck Depression Inventory-II	Beck Depression Inventory-II
	CRIS	CRIS	CRIS

\*patient and family or friend

Description of Measures

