#### Exploratory Generalization Measure

Generalization measures will be examined in a tertiary analysis to explore whether treatment effects generalize to everyday activities or participation in the community. Based on our previous study, treatment effect did not generalize to everyday activities as measured by the BRIEF-A. However, with the proposed methodological changes and the addition of functional practice with a Smartphone application, generalization to activities and community participation is anticipated to improve. The Metacognitive Index of the BRIEF-A was confirmed as a factor in our previous factor analysis and represents the executive function components targeted by GMT. The BRIEF-A was selected over the recommended common data element measure, the Frontal Systems Behavior Scale (FrSBe); since the FrSBe has not been tested in a homogenous TBI sample. While, our previous study did not reflect a significant improvement at the activity level, we will conduct a tertiary analysis to detect generalization using the BRIEF-A. In addition to the activity level of executive function, we would like to determine the effect of treatment at the community participation level. The TBI Outcomes Workgroup on common data elements (Wilde, 2010) has recommended the PART-O to measure participation in the community.

Behavior Rating Inventory of Executive Functions–Adult (BRIEF-A) is a self and informant report questionnaire consisting of 75 statements about executive behaviors. There are three possible responses to items: often, sometimes, never. There are nine subscales: inhibit, self-monitor, plan/organize, shift initiation, task monitor, emotional control, working memory, and organization of materials. Normative self-report (n=1,050) reliability ranges from .73 to .90 for the scales and .93 to .96 for Index and Global Executive Composite scores. While the reliability in a mixed clinical sample (n=233) ranged from .80 to .94 for scales and .96 to .98 for Index and Global Executive Composite scores. Test-retest reliability over 4 weeks averaged .82 to .93 on the scales and .94 for Index and Global Executive Composite

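### Informant training and weekly homework calls are described only for GMT, so the unmasked informant-rated BRIEF-A is open to differential expectation bias

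*Combined protocol and SAP*

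**What the plan says.** Section 6 (Procedures, Intervention) gives the informant two roles around GMT. Before it starts, "Friends or family members will participate in a training session prior to beginning GMT with the subject". While it runs, "The family member will be called each week during the GMT and asked to report whether the subject had an easy or difficulty time" with that week's homework.

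The control paragraph in the same section says that the Brain Health Workshop "was developed specifically for consistency with GMT session length and contact with the facilitator". The workshop comes "with homework and quizzes on information covered". It mentions no informant training and no calls to informants.

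The BRIEF-A "is a self and informant report questionnaire consisting of 75 statements about executive behaviors". Table 1 schedules it at pre-treatment, post-treatment and one month, with a footnote giving the respondents as "patient and family or friend". Section 4 says that the measure "will demonstrate whether improvements in simulated tasks generalize to overall functioning as observed by a proxy in the home". The patient chooses the informant, and a willing family member or friend is an inclusion criterion for everyone. No section says that informants are masked to arm or hypothesis.

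The BRIEF-A is the lead measure for the exploratory everyday-activities hypothesis (numbered 1.a in section 5 and 1.b in section 7). It is to be analysed in a tertiary analysis by paired t-tests. The plan does not say whether the self or the informant score is used.

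**The concern.** As the plan is written, informants in the GMT arm take part in a training session, are asked every week how the participant is coping, and then rate the participant's executive behaviour. Informants in the control arm are described only as raters. The arms therefore differ in how the outcome is measured as well as in treatment, and randomisation does not remove such a difference. A better informant score after GMT could reflect changed behaviour, a changed rater, or both.

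The stakes are limited but real. The investigators report that their previous study found no generalisation on the BRIEF-A, and they expect a better result here because of changed methods and functional practice. A positive informant result would be read as support for that. Section 5 also aims for procedures that can be carried into a later randomised trial, so the imbalance could be carried over with them.

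**Working it through.** There is no figure in the plan to reproduce: it gives no alpha, SD, effect size or power for the BRIEF-A. The check is a comparison of the text, followed by an illustration.

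**Step 1. The two arms side by side.**

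| Feature | GMT | Brain Health Workshop |
|---|---|---|
| Session length and facilitator contact | yes | matched by design |
| Homework | yes | yes |
| Informant training session | described | not described |
| Weekly informant call about homework | described | not described |
| Informant rates BRIEF-A | yes | yes |
| Informant masked | not stated | not stated |

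**Step 2. Number of contacts.** Table 2 gives 38 GMT and 16 control participants over 10 weeks. At one call a week, GMT has 38 × 10 = 380 calls and the control arm none described. Matching would need 16 × 10 = 160. These figures measure unequal contact, not bias.

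**Step 3. What a rater shift would do.** Assume no true effect, a shift of *b* SDs of the change score in GMT informants only, equal SDs in the two arms and a two-sided alpha of 0.05. None of these comes from the documents. False-positive rates follow from the noncentral t distribution.

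- Two-sample test, 38 v 16: noncentrality = b / √(1/38 + 1/16) = b / 0.298, with 38 + 16 − 2 = 52 df.
- Paired test within GMT, n = 38: noncentrality = b × √38 = b × 6.164, with 37 df.

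For b = 0.2 these give 0.2 / 0.298 = 0.67 and 0.2 × 6.164 = 1.23.

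| Assumed shift b (SD) | Two-sample, 38 v 16 | Paired, GMT n = 38 |
|---|---|---|
| 0 | 5.0% | 5.0% |
| 0.1 | 6.3% | 9.2% |
| 0.2 | 10.1% | 22.5% |
| 0.3 | 16.7% | 43.7% |
| 0.5 | 37.7% | 85.1% |

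**Step 4. Link to the planned test.** Section 7 names paired t-tests for the BRIEF-A and describes no comparison of arms. Read as a pre-post test within GMT, the whole shift enters the result with no control change to set against it. Matching informant contact would leave the right-hand column unchanged. It helps only when change is compared between arms, where the part of the shift common to both arms cancels.

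**The case against.** The strongest reply is that much of this rests on silence. The control paragraph is short and does not rule out informant contact. The content of the training session is not given. That the person trained and called is also the BRIEF-A rater is implied rather than stated. The measure is tertiary, it is also self-rated, and community participation is measured separately with the CRIS. Whether a control should match every component of a package is a design choice.

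These points limit the finding but do not remove it. Contact described for one arm and not for the other is naturally read as given to one arm only. The inclusion criteria require one family member or friend to give feedback, and no second informant role appears. If control informants do receive the same contact, the plan needs to say so.

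A reader might infer more than the text allows:

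- **That informants are told what should improve, or rehearse their ratings.** The documents do not say this. A report on whether homework was easy or hard is not a rehearsal of a 75-statement scale.
- **That the measure is biased towards GMT as a matter of fact.** Weekly questions about difficulty could also make informants notice more problems.
- **That the primary outcome is contaminated through extra home support.** The Tower of London is computerised and no informant rates it. The documents offer nothing to show such an effect.
- **That the informant baseline is taken after training.** Testing is placed before the 10-week period and training before GMT. The order of the two is not fixed, so this is a gap and not a demonstrated error.

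**Conclusion.** The point holds for the informant-rated BRIEF-A: unequal informant contact as described, with no masking stated, leaves that score open to differential expectation bias. The likelier direction favours GMT; the size is unknown, and the percentages above show only how a given shift would act. The conclusion assumes that the control arm has no informant contact beyond what is described, and that the trained and called person is the BRIEF-A rater. It does not extend to the self-rated BRIEF-A by this route, nor to the Tower of London. Because the measure is exploratory, the trial's main test is not at risk. What is at risk is any statement that benefit reaches daily life, in so far as it rests on "generalize to overall functioning as observed by a proxy in the home".

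**What to change.** 1. Collect the baseline informant BRIEF-A before any informant training, and state this order in Table 1 or under Procedures.
2. Make the same weekly homework call to informants in both arms, with one neutral script. The workshop already sets homework to ask about.
3. Compare change in BRIEF-A between arms, in place of the paired t-tests.
4. Report the self and informant scores separately.
5. State that the informant score is an unmasked rating, and that generalisation will not be claimed from it alone.

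The main cost is about 160 short calls at the Table 2 numbers, made by the staff who already call GMT informants; it rises in proportion if more controls are enrolled. The between-arm comparison is also less precise than a within-GMT test: with equal SDs, its standard error is 0.298 SD against 1/√38 = 0.162 SD, a ratio of 0.298 / 0.162 = 1.84. That is the price of having a control for rater effects.

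Some imbalance would remain, because the training session would still be given in GMT only and informants could still learn the arm. An equivalent control orientation could be added, but it would be a new procedure and its value is debatable. Item 5 covers what is left.
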